APPENDIX B. RATING SYSTEM FOR EFFECTIVE HEMOSTASIS

Excellent 1	o ICH:
(effective)	• Intracerebral hemorrhage: ≤ 20% increase in hematoma volume compared to baseline on a repeat CT or MRI scan performed at both the 1 and 12 hour post infusion time points.
	• Subarachnoid bleeding: ≤ 20% increase in maximum thickness using the most dense area on the follow-up vs. baseline at both the 1 and 12 hour post infusion time points.
	 Subdural hematoma: ≤ 20% increase in maximum thickness at both the 1 and 12 hour post infusion assessments compared to baseline.
	• Pericardial bleed. No increase in the size of pericardial effusion on repeat echocardiogram done within 12 hours of the end of infusion.
	• Intra-spinal bleed. No increase in hematoma size on repeat CT or MRI scan done within 12 hours of the end of infusion.
	• Other (e.g., gastrointestinal bleeding, genitourinary bleeding): ≤ 10% decrease in both corrected hemoglobin/hematocrit at 12 hours ^{2,3} compared to baseline.
Good 4	о ІСН:
(effective)	• Intracerebral hematoma: > 20% but ≤ 35% increase in hematoma volume compared to baseline on a repeat CT or MRI scan at +12-hour time point.
	• Subarachnoid bleeding: > 20% but < 35% increase in maximum thickness using the most dense area on the follow-up at +12 hours vs. baseline.
	• Subdural hematoma: > 20% but < 35% increase in maximum thickness at +12 hours compared to baseline.
	• Pericardial bleed. < 10% increase in the size of pericardial effusion on repeat echocardiogram done within 12 hours of the end of infusion.
	• Intra-spinal bleed. < 10% increase in hematoma size on repeat CT or MRI scan done within 12 hours of the end of infusion.
	• Other: $> 10\%$ to $\le 20\%$ decrease in both corrected hemoglobin/hematocrit at 12 hours compared to baseline. ^{2,3}

Poor/None 5	0	ICH:
(not effective)		• Intracerebral hematoma: > 35% increase in hematoma volume on a CT or MRI compared to baseline on a repeat CT or MRI scan at +12-hour time point.
		• Subarachnoid bleeding: > 35% increase in maximum thickness using the most dense area on the +12 hours vs. at baseline.
		• Subdural hematoma: > 35% increase in maximum thickness at +12 hours compared to baseline.
	•	Pericardial bleed. 10% or more increase in the size of pericardial effusion on repeat echocardiogram done within 12 hours of the end of infusion.
	•	Intra-spinal bleed. 10% or more increase in hematoma size on repeat CT or MRI scan done within 12 hours of the end of infusion.
	•	Other: > 20% decrease in both corrected hemoglobin/hematocrit. ^{2,3}

¹ For all types of bleeding: no additional plasma, blood products (whole blood products not including packed red blood cells [PRBCs]) and/or coagulation factor products required after initial treatment with andexanet.

² The smallest percentage decrease in hemoglobin or hematocrit should be used to determine the efficacy rating of excellent, good, or poor/none. The net change is defined as the difference between the corrected hemoglobin or hematocrit value at baseline and 12 hours after infusion.

³ For the adjusted hemoglobin and hematocrit calculation, it will be assumed that for each unit of PRBC transfusion there is an increase of 1 g/dL in hemoglobin and a 3% increase in hematocrit.

⁴ For all types of bleeding, no more than two additional units of plasma or blood products and/or coagulation factor products required after initial treatment with andexanet. "Blood products" include whole blood but not PRBCs.

⁵ For all types of bleeding, more than two additional units of plasma or blood products and/or coagulation factor products required after initial treatment with andexanet. "Blood products" include whole blood but not PRBCs.

APPENDIX C. GLASGOW COMA SCALE (GCS)

Score	Criterion
	Eye Opening
4	Open before stimulus
3	After spoken or shouted request
2	After fingertip stimulus
1	No opening at any time, no interfering factor
NT	Closed by local factor
	Verbal Response
5	Correctly gives name, place, and date
4	Not orientated but communication coherently
3	Intelligible single words
2	Only moans/groans
1	No audible response, nom interfering factor
NT	Factor interfering with communication
	Best Motor Response
6	Obey 2-part request
5	Brings hand above clavicle to stimulus on head/neck
4	Bends arm at elbow rapidly but features not predominantly abnormal
3	Bends arm at elbow, features clearly predominantly abnormal
2	Extends arm at elbow
1	No movement in arms/legs, no interfering factor
NT	Paralyzed or other limiting factor

NT = Not testable

APPENDIX D. MODIFIED RANKIN SCORE (MRS)

Score	Description
0	No symptoms at all
1	No significant disability despite symptoms; able to carry out all usual duties and activities
2	Slight disability; unable to carry out all previous activities, but able to look after own affairs without assistance
3	Moderate disability; requiring some help, but able to walk without assistance
4	Moderately severe disability; unable to walk without assistance and unable to attend to own bodily needs without assistance
5	Severe disability; bedridden, incontinent, and requiring constant nursing care and attention
6	Dead

APPENDIX E. DISSEMINATED INTRAVASCULAR COAGULATION (DIC) SCORING ALGORITHM [28]

Laboratory Test	Result	Score
Platelet Count	$\geq 100 \times 10^9 / L$	0
	< 100 x 10 ⁹ / L	1
	$< 50 \times 10^9 / L$	2
D-Dimer, Fibrin Degradation Products	No increase	0
	Moderate increase	2
	Strong increase	3
Prothrombin Time	< 3 seconds	0
	\geq 3 but < 6 seconds	1
	≥ 6 seconds	2
Fibrinogen Level	≥ 1 g/L	0
	< 1 g/L	1

Note: Algorithm should only be used for patients with an underlying disorder known to be associated with overt DIC. A score of ≥ 5 is compatible with overt DIC.

APPENDIX F. DEFINITIONS OF SEVERE SEPSIS AND SEPTIC SHOCK [29]

Severe sepsis is defined as sepsis-induced tissue hypoperfusion or organ dysfunction with any of the following thought to be due to the infection:

- Sepsis-induced hypotension
- Lactate above Upper Limits of laboratory Normal (ULN)
- Urine output < 0.5 mL/kg/hr for more than two hours despite adequate fluid resuscitation
- Acute lung injury with $PaO_2/FIO_2 < 250$ in the absence of pneumonia as infection source
- Acute lung injury with $PaO_2/FIO_2 < 200$ in the presence of pneumonia as infection source
- Creatinine > 2 mg/dL (176.8 micromol/L)
- Bilirubin > 4 mg/dL (34.2 micromol/L)
- Platelet count $< 100,000 \text{ microL}^{-1}$
- Coagulopathy (International Normalized Ratio [INR] > 1.5)

Sepsis-induced tissue hypoperfusion is defined as infection-induced hypotension, elevated lactate, or oliguria.

Sepsis-induced hypotension is defined as a systolic blood pressure (SBP) < 90 mmHg, or Mean Arterial Pressure (MAP) < 70 mmHg, or a SBP decrease > 40 mmHg, or less than two standard deviations below normal for age in the absence of other causes of hypotension.

Septic shock is defined as sepsis-induced hypotension (as defined above) persisting despite adequate fluid resuscitation.

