4.2. Exclusion Criteria

If a patient meets any of the following criteria, he or she is *not* eligible to participate:

- 1. The patient is scheduled to undergo surgery in less than 12 hours after end of and exanet infusion, with the exception of minimally invasive surgery/procedures (e.g., endoscopy, bronchoscopy, central lines, Burr holes see more examples in Appendix G).
- 2. A patient with ICH has any of the following:
 - a. Glasgow coma score < 7.
 - b. Estimated intracerebral hematoma volume > 60 cc as assessed by the CT or MRI.
- 3. Patients with visible, musculoskeletal, or intra-articular bleeding as the qualifying bleed.

- 4. The patient has an expected survival of less than 1 month.
- 5. The patient has a recent history (within 2 weeks) of a diagnosed Thrombotic Event (TE) as follows: Venous Thromboembolism (VTE; e.g., deep venous thrombosis, pulmonary embolism, cerebral venous thrombosis), myocardial infarction (including an isolated troponin elevation), disseminated intravascular coagulation (DIC), cerebral vascular accident, transient ischemic attack, unstable angina pectoris hospitalization, or severe peripheral vascular disease within 2 weeks prior to Screening (see Appendix E for DIC scoring algorithm).
- 6. The patient has severe sepsis or septic shock at the time of Screening (see definition Appendix F).
- 7. The patient is pregnant or a lactating female.
- 8. The patient has received any of the following drugs or blood products within 7 days or Screening:
 - a. Vitamin K Antagonist (VKA) (e.g., warfarin).
 - b. Dabigatran.
 - c. Prothrombin Complex Concentrate products (PCC, e.g., Kcentra®) or recombinant factor VIIa (rfVIIa) (e.g., NovoSeven®).
 - d. Whole blood, plasma fractions.
 - e. Note: Administration of platelets or Packed Red Blood Cells (PRBCs) is not an exclusion criterion.
- 9. The patient was treated with an investigational drug < 30 days prior to Screening.
- 10. Planned administration of PCC, Fresh Frozen Plasma (FFP), or rfVIIa from Screening until within 12 hours after the end of the andexanet infusion.

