10.2.3. Clinical Laboratory Testing

Blood specimens for routine chemistry and hematology and other biomarkers will be obtained at selected time points (see Appendix A). The following assays will be performed at the Local Laboratory for inclusion criteria, clinical monitoring, and routine safety:

Hematology:	Hemoglobin, hematocrit, white blood cell (WBC), platelet count.		
Coagulation:	International normalized ratio (INR).		
Serum Chemistry:	Sodium, potassium, chloride, carbon dioxide (bicarbonate), glucose, blood urea nitrogen (BUN), creatinine, aspartate aminotransferase (AST), alanine aminotransferase (ALT), albumin, alkaline phosphatase, calcium, phosphorus, and total, direct, and indirect bilirubin.		
Serum or Urine Pregnancy Test:	In women		

The following assays will be performed at a Central Laboratory:

Purpose	Assays	
Critical Efficacy Assays	Anti-fXa activity	
	Thrombin generation (TG)	
	Anticoagulant free fraction (for direct FXa inhibitors)	
Immunogenicity Assays	Antibodies to and exanet, FX, and FXa; neutralizing antibody (nAb) activity	
Exploratory Efficacy Assays	Total and free TFPI	
	ATIII antigen	
	Anti-fIIa activity	

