5.9. Data Derivation

- The following derivation rules will apply: unless missing data is imputed using the
 imputation methods described above, all tabulations involving change from baseline data
 will only include subjects with cohort data i.e. with data at baseline and at follow-up.
 Change from baseline will be calculated as follow-up values minus baseline value.
 Percentage changes from baseline will be rounded to 1 decimal place.
- For analysis purposes, 1 month = 30 days and duration in months will be rounded to 1 decimal place.
- Any derived data recorded in hours will be rounded to 1 decimal place.
- All calculation of length of time, including age, should be performed using SAS function to account for leap year.
- Height in inches will be converted to centimeters by multiplying by 2.54 and rounding to the nearest integer.
- Weight in lbs will be converted to kg by dividing by 2.2046 and rounding to 1 decimal place.
- Body mass index (BMI) will be calculated as weight (kg) / (height (cm)/100)² rounded to 1 decimal place.
- Temperature in Fahrenheit will be converted to Celsius by subtracting 32 and dividing by 1.8.

- Hemoglobin in g/L will be converted to mmol/L by multiplying by 0.06206 and rounding to 2 decimal places.
- To convert from g/dL to g/L multiply by 10.
- To convert from mg/dL to g/L multiply by 0.01 and round to 2 decimal places.
- To convert from mEq/L to mmol/L multiply by 1.
- To convert from µkat/L to U/L multiply by 1.
- For white blood cell and platelet count then $10^9/L = 10^3/\text{mm}^3$.
- For each white blood cell differential (Neutrophils, Lymphocytes, Monocytes, Eosinophils, Basophils) to convert from % to 10⁹/L by multiplying the value by the WBC (10⁹/L) and dividing by 100 and rounding to 1 decimal place.
- For creatinine to convert from μmol/L to mg/dL divide by 88.4173 and round to 1 decimal place.
- For serum glucose to convert from mmol/L to mg/dL divide by 0.0555 and round to 1 decimal place.
- For blood urea nitrogen to convert from mmol/L to mg/dL divide by 0.3651 and round to 1 decimal place.
- For total and direct bilirubin to convert from μmol/L to mg/dL to μmol/L divide by 17.0999 and round to 1 decimal place.
- For calcium to convert from mmol/L to mg/dL divide by 0.2495 and round to 2 decimal places.
- For phosphorous to convert from mmol/L to mg/dL divide by 0.3229 and round to 2 decimal places.
- For plasma concentrations that are lower than lower level of quantification (LLOQ) then

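### Appendix F prints two bilirubin limits for severe sepsis, 4 mg/dL and 34.2 micromol/L, that differ by a factor of 2, so eligibility under exclusion 6 can depend on the reporting unit

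*Protocol*

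**What the plan says.** Protocol section 4.2, criterion 6, excludes a patient when "The patient has severe sepsis or septic shock at the time of Screening" and sends the reader to Appendix F for the definition. The synopsis carries the same criterion.

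Appendix F defines severe sepsis as tissue hypoperfusion caused by sepsis, or "organ dysfunction with any of the following thought to be due to the infection", followed by nine items. Any one item is enough. Two of them are chemistry limits printed in both conventional and SI units:

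- "Creatinine > 2 mg/dL (176.8 micromol/L"
- "Bilirubin > 4 mg/dL (34.2 micromol/L"

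Protocol section 10.2.3 places bilirubin among the tests covered by this statement: "The following assays will be performed at the Local Laboratory for inclusion criteria, clinical monitoring, and routine safety". Appendix A schedules that chemistry in the three hours before the bolus.

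SAP section 5.9 gives conversion factors for both analytes. For bilirubin the instruction is to "divide by 17.0999 and round to 1 decimal place"; for creatinine it is "For creatinine to convert from μmol/L to mg/dL divide by 88.4173 and round to 1 decimal". SAP section 4.2.8 lists total bilirubin in micromol/L but creatinine in mg/dL.

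**The concern.** A limit printed in two units is meant to be one limit. If the two figures disagree, whoever applies the criterion is using one of two different rules without knowing it. Which rule is used depends on something unrelated to the patient, namely the unit on the local laboratory report.

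This matters more than a slip in background text because Appendix F is the working definition behind an exclusion criterion. A single item attributed to infection is enough to exclude, so bilirubin alone can decide the matter. Up to 120 sites in North America, Europe and Japan use their own laboratories. The SAP also carries a bilirubin unit conversion, which suggests that results were expected in more than one unit.

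At stake is consistent eligibility between sites and, downstream, consistent classification of treated patients in two SAP outputs: the list of patients meeting an exclusion criterion (section 5.10.3) and the list of protocol deviations (section 5.10.4), which includes patients who entered without satisfying the entry criteria.

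**Working it through.** **Inputs**

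- Bilirubin limit, conventional unit: 4 mg/dL (protocol Appendix F).
- Bilirubin limit, SI unit: 34.2 micromol/L (same line).
- Bilirubin factor: 17.0999 micromol/L per mg/dL (SAP 5.9).
- Creatinine limit: 2 mg/dL, paired with 176.8 micromol/L (protocol Appendix F).
- Creatinine factor: 88.4173 micromol/L per mg/dL (SAP 5.9).

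The bilirubin sentence in SAP 5.9 is garbled about direction, since it names micromol/L both as the starting and as the finishing unit. Division by 17.0999 makes sense only when going from micromol/L to mg/dL, and I use it that way.

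**Formula**

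micromol/L = mg/dL × factor; mg/dL = micromol/L ÷ factor.

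**Control: the creatinine line**

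2 × 88.4173 = 176.83, which reproduces the printed 176.8. In reverse, 176.8 ÷ 88.4173 = 2.00. The method therefore recovers the protocol's figure where the pair is sound.

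**Bilirubin line**

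- 4 × 17.0999 = 68.40 micromol/L, against 34.2 printed.
- 34.2 ÷ 17.0999 = 2.00 mg/dL, against 4 printed.
- 68.40 ÷ 34.2 = 2.00, the ratio of the two limits.
- 34.2 ÷ 4 = 8.55, the factor that the printed pair implies, which is half the SAP factor.

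**Sensitivity to the factor**

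With 17.1 the results are 68.4 micromol/L and 2.0 mg/dL. With 17.104 they are 68.416 micromol/L and 1.9995 mg/dL. Rounding of the factor does not explain the gap.

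**Who is affected**

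| Infection-attributed bilirubin | Under the mg/dL figure | Under the SI figure |
|---|---|---|
| up to 34.2 micromol/L (2.0 mg/dL) | item not met | item not met |
| above 34.2, up to 68.4 micromol/L (above 2.0, up to 4.0 mg/dL) | item not met | item met |
| above 68.4 micromol/L (4.0 mg/dL) | item met | item met |

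For example, 3 mg/dL is 3 × 17.0999 = 51.3 micromol/L: below the first limit and above the second. The disagreement always runs in this direction, whichever figure was intended. What the intended figure decides is which group of sites has been misclassifying, not which group is stricter. The middle row changes a patient's eligibility only if no other Appendix F item is present.

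**The case against.** The arithmetic is hard to contest, and nothing elsewhere in the documents reconciles the pair. The fair objections concern how far it reaches.

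- **One item of nine.** Lactate, urine output, hypotension, lung injury (two items), creatinine, platelets and INR each qualify independently, and every item must be judged due to the infection. A reader might infer that the sepsis exclusion as a whole is twice as strict at SI-unit sites. The documents do not support that: one cut-off is halved, which says nothing about how many more patients are excluded. This objection stands.
- **Region.** A reader might infer that the error selects different populations by region and so distorts the SAP's regional summaries. The documents say only that chemistry is done locally. They do not say which sites report bilirubin in SI units, whether units follow region, or which of the two figures a site would use. The effect is possible, not shown.
- **The listing.** A reader might infer that the section 5.10.3 listing is wrong. That section does not say whether the listing comes from investigator entries or from laboratory values, and no treated patient in the affected band is identified. Patients turned away before treatment would not appear in it at all, since it covers treated patients only.
- **Safety purpose.** The design discussion in protocol sections 3.4.2 and 3.5 gives safety reasons for excluding recent thrombotic events and recent procoagulant products, but none for sepsis. It would go too far to say that a documented safety rationale has been undermined.
- **Timing.** SAP section 1.0 describes 477 locked patients. An amendment cannot alter their eligibility. This stands too, and it moves the useful action to clarification and classification.

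What remains is that an eligibility definition in force gives two different limits for one laboratory value.

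**Conclusion.** The discrepancy is real and certain as printed: the two bilirubin limits in Appendix F differ by a factor of 2. Its consequence is conditional. It changes eligibility only for a patient whose bilirubin lies above 34.2 and up to 68.4 micromol/L, in whom the rise is attributed to infection, who has no other qualifying item, and whose site applies the SI figure rather than the mg/dL figure. The documents give no count of such patients, so the size of the effect on enrolment cannot be stated.

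It does not touch the trial's main conclusions. The sample size, the Efficacy Population (adjudicated bleeding criteria plus baseline anti-fXa level, SAP 5.2.2), the Safety Population (any amount of drug received, SAP 5.2.1) and the primary analyses (SAP 5.13.1) do not use this line.

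The documents alone do not show which figure was intended, and this review does not take a view on it. The conclusion assumes that the SAP factor is the right one to apply, which the creatinine control and the alternative bilirubin factors support, and that the text was read correctly from the page. Severity: minor.

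**What to change.** **Text.** The sponsor should reconcile the bilirubin line in Appendix F so that both units state one limit, through a protocol amendment or a clarification memo. As arithmetic only, 4 mg/dL pairs with 68.4 micromol/L, and 34.2 micromol/L pairs with 2.0 mg/dL; the sponsor must decide which was meant. The bilirubin conversion sentence in SAP 5.9 should be tidied at the same time so that it states one direction.

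**Patients already treated.** Use the single reconciled limit when classifying exclusion 6 for the listings in SAP 5.10.3 and 5.10.4:

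1. Flag treated patients with pre-dose total bilirubin above 34.2 and up to 68.4 micromol/L. SAP 4.2.8 already includes this variable.
2. For those flagged, check source records for infection and for attribution of the raised bilirubin to it. Bilirubin alone cannot establish severe sepsis, and the medical-history variables in SAP 4.2.2 do not include infection.
3. Classify each patient against the reconciled limit and list accordingly.

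**Cost.** A one-line correction, a short program to flag patients, and a small amount of record review. No primary analysis needs to be rerun.

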APPENDIX G. EXAMPLES OF MINOR PROCEDURES ALLOWED

- Burr holes (trepanation)
- Arthroscopy
- Thoracentesis
- Pericardial puncture/drainage
- Embolization
- Endoscopy with cauterization/embolization
- Cystoscopy
- Laparocentesis
- Lumbar puncture
- Colonoscopy
- Radiofrequency ablation of coronary isthmus
- Angiography
- Cardiac catheterization
- CT-guided abscess drainage
- Knee arthrocentesis

APPENDIX H. NATIONAL INSTITUTES OF HEALTH STROKE SCALE (NIHSS)

5.3.5.1 Study Reports of Controlled Clinical Studies Portola Pharmaceuticals, Inc.

N		 	_
ST	RC	K	Έ
S	ΞA	L	E

Patient Ide	ntification			
	Pt. Date of Birth	/	/	
Hospital		()
	Date of Exam	1	1	

Interval: [] Baseline [] 2 hours post treatment [] 3 months [] Other	[] 24 hours post onset of symptoms ±20 minutes	[] 7-10 days
Time:: []am []pm		
Person Administering Scale		

Administer stroke scale items in the order listed. Record performance in each category after each subscale exam. Do not go back and change scores. Follow directions provided for each exam technique. Scores should reflect what the patient does, not what the clinician thinks the patient can do. The clinician should record answers while administering the exam and work quickly. Except where indicated, the patient should not be coached (i.e., repeated requests to patient to make a special effort).

Instructions Scale Definition Score Level of Consciousness: The investigator must choose a 0 = Alert; keenly responsive. response if a full evaluation is prevented by such obstacles as an 1 = **Not alert**; but arousable by minor stimulation to obey, endotracheal tube, language barrier, orotracheal trauma/bandages. A answer, or respond. 3 is scored only if the patient makes no movement (other than reflexive 2 = Not alert; requires repeated stimulation to attend, or is posturing) in response to noxious stimulation. obtunded and requires strong or painful stimulation to make movements (not stereotyped). 3 = Responds only with reflex motor or autonomic effects or totally unresponsive, flaccid, and areflexic. 1b. LOC Questions: The patient is asked the month and his/her age. 0 = Answers both questions correctly. The answer must be correct - there is no partial credit for being close. Aphasic and stuporous patients who do not comprehend the questions Answers one question correctly. will score 2. Patients unable to speak because of endotracheal intubation, orotracheal trauma, severe dysarthria from any cause, Answers neither question correctly. language barrier, or any other problem not secondary to aphasia are given a 1. It is important that only the initial answer be graded and that the examiner not "help" the patient with verbal or non-verbal cues. 1c. LOC Commands: The patient is asked to open and close the 0 = **Performs** both tasks correctly. eyes and then to grip and release the non-paretic hand. Substitute another one step command if the hands cannot be used. Credit is 1 = **Performs** one task correctly. given if an unequivocal attempt is made but not completed due to weakness. If the patient does not respond to command, the task 2 = **Performs** neither task correctly. should be demonstrated to him or her (pantomime), and the result scored (i.e., follows none, one or two commands). Patients with trauma, amputation, or other physical impediments should be given suitable one-step commands. Only the first attempt is scored. 2. Best Gaze: Only horizontal eye movements will be tested. 0 = Normal.Voluntary or reflexive (oculocephalic) eye movements will be scored, but caloric testing is not done. If the patient has a conjugate 1 = Partial gaze palsy; gaze is abnormal in one or both eyes, deviation of the eyes that can be overcome by voluntary or reflexive but forced deviation or total gaze paresis is not present. activity, the score will be 1. If a patient has an isolated peripheral nerve paresis (CN III, IV or VI), score a 1. Gaze is testable in all 2 = Forced deviation, or total gaze paresis not overcome by the aphasic patients. Patients with ocular trauma, bandages, pre-existing oculocephalic maneuver. blindness, or other disorder of visual acuity or fields should be tested with reflexive movements, and a choice made by the investigator. Establishing eye contact and then moving about the patient from side to side will occasionally clarify the presence of a partial gaze palsy.

Rev 10/1/2003

5.3.5.1 Study Reports of Controlled Clinical Studies Portola Pharmaceuticals, Inc.

N		ŀ	_
STF	₹C	K	Έ
\overline{SC}	Α	L	Ē

Patient Ide	ntification			
	Pt. Date of Birth	/	/	
Hospital		(-)
	Date of Evam	1	1	

JUNEE	Date of Exam/	
Interval: [] Baseline [] 2 hours post treatment [] 24 ho	ours post onset of symptoms ±20 minutes [] 7-10 days	
3. Visual: Visual fields (upper and lower quadrants) are tested by confrontation, using finger counting or visual threat, as appropriate. Patients may be encouraged, but if they look at the side of the moving fingers appropriately, this can be scored as normal. If there is unilateral blindness or enucleation, visual fields in the remaining eye are scored. Score 1 only if a clear-cut asymmetry, including quadrantanopia, is found. If patient is blind from any cause, score 3. Double simultaneous stimulation is performed at this point. If there is extinction, patient receives a 1, and the results are used to respond to item 11.	 0 = No visual loss. 1 = Partial hemianopia. 2 = Complete hemianopia. 3 = Bilateral hemianopia (blind including cortical blindness). 	
4. Facial Palsy: Ask – or use pantomime to encourage – the patient to show teeth or raise eyebrows and close eyes. Score symmetry of grimace in response to noxious stimuli in the poorly responsive or non-comprehending patient. If facial trauma/bandages, orotracheal tube, tape or other physical barriers obscure the face, these should be removed to the extent possible.	 0 = Normal symmetrical movements. 1 = Minor paralysis (flattened nasolabial fold, asymmetry on smiling). 2 = Partial paralysis (total or near-total paralysis of lower face). 3 = Complete paralysis of one or both sides (absence of facial movement in the upper and lower face). 	
5. Motor Arm: The limb is placed in the appropriate position: extend the arms (palms down) 90 degrees (if sitting) or 45 degrees (if supine). Drift is scored if the arm falls before 10 seconds. The aphasic patient is encouraged using urgency in the voice and pantomime, but not noxious stimulation. Each limb is tested in turn, beginning with the non-paretic arm. Only in the case of amputation or joint fusion at the shoulder, the examiner should record the score as untestable (UN), and clearly write the explanation for this choice.	 0 = No drift; limb holds 90 (or 45) degrees for full 10 seconds. 1 = Drift; limb holds 90 (or 45) degrees, but drifts down before full 10 seconds; does not hit bed or other support. 2 = Some effort against gravity; limb cannot get to or maintain (if cued) 90 (or 45) degrees, drifts down to bed, but has some effort against gravity. 3 = No effort against gravity; limb falls. 4 = No movement. UN = Amputation or joint fusion, explain: 5a. Left Arm 5b. Right Arm 	
6. Motor Leg: The limb is placed in the appropriate position: hold the leg at 30 degrees (always tested supine). Drift is scored if the leg falls before 5 seconds. The aphasic patient is encouraged using urgency in the voice and pantomime, but not noxious stimulation. Each limb is tested in turn, beginning with the non-paretic leg. Only in the case of amputation or joint fusion at the hip, the examiner should record the score as untestable (UN), and clearly write the explanation for this choice.	 0 = No drift; leg holds 30-degree position for full 5 seconds. 1 = Drift; leg falls by the end of the 5-second period but does not hit bed. 2 = Some effort against gravity; leg falls to bed by 5 seconds, but has some effort against gravity. 3 = No effort against gravity; leg falls to bed immediately. 4 = No movement. UN = Amputation or joint fusion, explain: 6a. Left Leg 6b. Right Leg 	
		_

5.3.5.1 Study Reports of Controlled Clinical Studies Portola Pharmaceuticals, Inc.

N		ŀ	_
STF	₹C	K	Έ
\overline{SC}	Α	L	Ē

Patient Ide	ntification			
	Pt. Date of Birth	/	/	
Hospital		()
	Date of Exam	1	1	

	Hospital(-
SCALE	Date of Exam /	/
Interval: [] Baseline [] 2 hours post treatment [] 24 hours post treatment [] 25 hours post treatment [] 26 hours post treatment [] 27 hours post treatment [] 28 hours post treatment [] 28 hours post treatment [] 29 hours post treatment [] 29 hours post treatment [] 20 hours post post post post post post post pos		7
7. Limb Ataxia: This item is aimed at finding evidence of a unilateral cerebellar lesion. Test with eyes open. In case of visual defect, ensure testing is done in intact visual field. The finger-nose-finger and heel-shin tests are performed on both sides, and ataxia is scored only if present out of proportion to weakness. Ataxia is absent in the patient who cannot understand or is paralyzed. Only in the case of amputation or joint fusion, the examiner should record the score as untestable (UN), and clearly write the explanation for this choice. In case of blindness, test by having the patient touch nose from extended arm position.	0 = Absent. 1 = Present in one limb. 2 = Present in two limbs. UN = Amputation or joint fusion, explain:	
8. Sensory: Sensation or grimace to pinprick when tested, or withdrawal from noxious stimulus in the obtunded or aphasic patient. Only sensory loss attributed to stroke is scored as abnormal and the examiner should test as many body areas (arms [not hands], legs, trunk, face) as needed to accurately check for hemisensory loss. A score of 2, "severe or total sensory loss," should only be given when a severe or total loss of sensation can be clearly demonstrated. Stuporous and aphasic patients will, therefore, probably score 1 or 0. The patient with brainstem stroke who has bilateral loss of sensation is scored 2. If the patient does not respond and is quadriplegic, score 2. Patients in a coma (item 1a=3) are automatically given a 2 on this item.	 0 = Normal; no sensory loss. 1 = Mild-to-moderate sensory loss; patient feels pinprick is less sharp or is dull on the affected side; or there is a loss of superficial pain with pinprick, but patient is aware of being touched. 2 = Severe to total sensory loss; patient is not aware of being touched in the face, arm, and leg. 	
9. Best Language: A great deal of information about comprehension will be obtained during the preceding sections of the examination. For this scale item, the patient is asked to describe what is happening in the attached picture, to name the items on the attached naming sheet and to read from the attached list of sentences. Comprehension is judged from responses here, as well as to all of the commands in the preceding general neurological exam. If visual loss interferes with the tests, ask the patient to identify objects placed in the hand, repeat, and produce speech. The intubated patient should be asked to write. The patient in a coma (item 1a=3) will automatically score 3 on this item. The examiner must choose a score for the patient with stupor or limited cooperation, but a score of 3 should be used only if the patient is mute and follows no one-step commands.	0 = No aphasia; normal. 1 = Mild-to-moderate aphasia; some obvious loss of fluency or facility of comprehension, without significant limitation on ideas expressed or form of expression. Reduction of speech and/or comprehension, however, makes conversation about provided materials difficult or impossible. For example, in conversation about provided materials, examiner can identify picture or naming card content from patient's response. 2 = Severe aphasia; all communication is through fragmentary expression; great need for inference, questioning, and guessing by the listener. Range of information that can be exchanged is limited; listener carries burden of communication. Examiner cannot identify materials provided from patient response. 3 = Mute, global aphasia; no usable speech or auditory comprehension.	
10. Dysarthria: If patient is thought to be normal, an adequate sample of speech must be obtained by asking patient to read or repeat words from the attached list. If the patient has severe aphasia, the clarity of articulation of spontaneous speech can be rated. Only if the patient is intubated or has other physical barriers to producing speech, the examiner should record the score as untestable (UN), and clearly write an explanation for this choice. Do not tell the patient why he or she is being tested.	0 = Normal. 1 = Mild-to-moderate dysarthria; patient slurs at least some words and, at worst, can be understood with some difficulty. 2 = Severe dysarthria; patient's speech is so slurred as to be unintelligible in the absence of or out of proportion to any dysphasia, or is mute/anarthric. UN = Intubated or other physical barrier, explain:	

	1			A 1	10
An	$\alpha\epsilon$	exa:	net	Α	Ita

[figure not shown]
N I H STROKE SCALE

5.3.5.1	Study	Reports	of	Contro	olled	Clinical Stu	ıdies
			P	ortola I	Pharr	naceuticals	Inc

NIH	Patient Identification	
STROKE	Pt. Date of Birth/	
rval: [] Baseline [] 2 hours post treatment [] 24 hours post onset of [] 3 months [] Other	Hospital()
SCALE	Date of Exam /	/
11. Extinction and Inattention (formerly Neglect): Sufficient	0 = No abnormality.	
testing. If the patient has a severe visual loss preventing visual double simultaneous stimulation, and the cutaneous stimuli are normal, the score is normal. If the patient has aphasia but does	1 = Visual, tactile, auditory, spatial, or personal inattention or extinction to bilateral simultaneous stimulation in one of the sensory modalities.	

Extinction and Inattention (formerly Neglect): Sufficient information to identify neglect may be obtained during the prior testing. If the patient has a severe visual loss preventing visual double simultaneous stimulation, and the cutaneous stimuli are normal, the score is normal. If the patient has aphasia but does appear to attend to both sides, the score is normal. The presence of visual spatial neglect or anosagnosia may also be taken as evidence of abnormality. Since the abnormality is scored only if present, the item is never untestable.

- 1 = Visual, tactile, or extinction of the sensor
- 2 = Profound hemi-inattention or extinction to more than one modality; does not recognize own hand or orients to only one side of space.

Protocol 14-505 Amendment 6 30 November 2018

[figure not shown]
You know how.

Down to earth.

I got home from work.

Near the table in the dining room.

They heard him speak on the radio last night.

Protocol 14-505 Amendment 6 30 November 2018

MAMA

TIP - TOP

FIFTY - FIFTY

THANKS

HUCKLEBERRY

BASEBALL PLAYER

